# **Product Use**

#### Baseline and Product Use Period 1 (Days -2 to 29, Test Visits 1-3):

Subjects who meet study requirements following screening will be scheduled to check in to the clinic for Test Visit 1 on Day -2 (check-in for JUUL® arm will be as early in the day as possible to maximize the time to use the product) and will remain in the clinic until completion of all study events. Subjects who fail the check-in requirements will be considered a "screen failure" and will be excluded from participation. For the *my*bluTM and continue-smoking arms, the Baseline Period will consist of the time between check-in and first product use on Day 1.

Following discharge from Test Visit 1 (Day 5), subjects in the *my*bluTM and continue-smoking arms will follow the product use requirements of their randomization arm and will report product use daily. All subjects in the *my*bluTM and continue-smoking arms will be required to present to the clinic site on Day 14 and Day 28 (each ± 2 days) for Test Visits 2 and 3, respectively. Test Visit 2 will be ambulatory and primarily for the return and dispensing of test products for the *my*bluTM arm and for compliance and safety checks for both study arms. Test Visit 3 (Days 28 and 29) will be for these purposes in addition to completion of the endpoint assessments during confinement.

#### Product Use Period 2 (Days 30 to 57, Test Visits 4 and 5):

Following discharge from Test Visit 3, subjects in the *my*blu™ and continue-smoking arms will follow the product use requirements of their randomization arm and will report product use daily. All subjects in both arms will be required to present to the

clinic site on Day 42 and Day 56 (each  $\pm$  2 days) for Test Visits 4 and 5, respectively. Test Visit 4 will be ambulatory and primarily for the return and dispensing of test products for the mybluTM arm and for compliance and safety checks for both study arms. Test Visit 5 will be for these purposes in addition to completion of the endpoint assessments during confinement. Subjects will be discharged from the clinical portion of the study at the end of Test Visit 5.

#### 4. ANALYSIS POPULATIONS

#### 4.1 Analysis Populations

#### 4.1.1 Safety Population

The safety population will include all subjects with at least one reported product use from Day -1.

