Abbreviations: AE = Adverse event, BoE = Biomarker of exposure, BoPH = Biomarker of potential harm, CO = Carbon monoxide, ECG = Electrocardiogram, FeNO = Fractional concentration of exhaled nitric oxide, MTWS-R = Minnesota Nicotine Withdrawal Scale-Revised, PES = Product Evaluation Scale, PSCDI = Penn State Cigarette Dependence Index, PSECDI = Penn State Electronic Cigarette Dependence Index, QSU-Brief = Questionnaire of Smoking Urges-Brief.

Table 3 Study Events for Baseline through Follow-up Periods – JUUL[®] Arm

Study Day	-2 ¹	-1	1	15
EVENTS/ASSESSMENTS				(±2)
Confinement	Х	х	Х	
Review of Applicable Inclusion/Exclusion Criteria	Х			
Reminder Telephone Calls ²	Х			
Additional Demographics Documentation	Х			
Usual Brand Combustible Cigarette Documentation	X ³			
Tobacco/Nicotine Use History Questionnaire	X ³			
Provide Smoking Cessation Information			X ⁴	
Safety and Compliance Events		•		
Medical History	X ³			
Concomitant Medication Reporting	Х	Х	X ⁴	Х
Symptom-driven Physical Examination	Х		X ⁴	
Body Weight	Х			
Urinalysis	Х			
Clinical Chemistry and Hematology	Х			
Urine Cotinine Test	Х			
Urine Drug Test	Х			
Alcohol Breath Test	Х			
Urine Pregnancy Test (females)	Х			
Exhaled CO	Х			
Vital Signs	Х		X ⁴	
12-lead ECG			X ⁴	
AE Reporting	Х	Х	X ⁴	Х
Product Use Documentation and Assessments				
Review of Tobacco and Nicotine Restrictions	Х			
Test Product Demonstration	Х			
Product Use ⁵	Х	Х		
Nicotine PK Assessments				
Product Use ⁶			Х	
Pod Weight Documentation ⁷			Х	
Blood Sampling ⁸			X	
Urge to Smoke Assessment ⁹			X	

¹ Subjects should check-in to the clinic as early as possible on Day -2.

² The clinic staff will make a telephone call within 24 - 48 hours prior to the scheduled visits to remind subjects of the date and time of the upcoming Test Visit.

³ Updated as necessary.

- ⁴ Or upon early termination.
- ⁵ All subjects will use the assigned study product from completion of check-in events through discharge from the study.
- ⁶ Two product use sessions: fixed puffing regimen in the morning and an ad libitum regimen in the afternoon.
- ⁷ Pods will be weighed prior to and following use.
- ⁸ Blood samples for nicotine concentration measurement will take place approximately 5 minutes prior to and at 3, 5, 7, 10, 12, 15, 20, 30, 60, 120 and 180 minutes following the start of each product use episode.

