6.9.2 Reporting

Events reported prior to use of study products on Day -2 will be documented as baseline signs and symptoms in the medical history. All events occurring after use of study products on Day -2 must be recorded on the eCRF as AEs. Documentation will include the date and time of onset, action taken, outcome (resolved, improved, unchanged, worse, fatal, or unknown/lost to follow-up), duration, relationship to product administration, and severity for each event. AEs will be coded using most current version of the Medical Dictionary for Regulatory Activities (MedDRA)[®] available at

The Investigator will review each event and assess its relationship to product administration as unrelated, unlikely, possibly, probably, or likely.

In addition, each sign or symptom reported will be graded on a 3-point severity scale using mild, moderate, or severe.

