7.6 Safety

All clinical safety data will be listed by subject and time point and summarized as described in the SAP.

All reported events captured in the database will be listed in by-subject data listings. However, only study product use-emergent AEs. A study product use-emergent AE is defined as an AE that is starting or worsening at the time of or after the first study product use on Day -2.

Frequencies of subjects with study product use-emergent AEs, regardless of relationship to study product will be summarized and sorted by system organ class. Frequencies of subjects

with study product use-emergent SAEs will be likewise summarized. Frequencies of study product use-emergent AEs will be summarized by severity and relationship to study product.

Changes in physical examinations (if any) will be described in the text of the final report.

All prior and concomitant medications recorded during the study will be listed by subject.

The following pre- and post-bronchodilator lung function variables will be summarized.

- Measured and percent of predicted FEV₁
- Measured and percent of predicted FVC
- Measured and percent of predicted FEV₁:FVC ratio
- Measured and percent of predicted FEF_{25-75%}

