Screening of subjects will occur within 28 days prior to prior to check-in (Day -2) for Test Visit 1. Screening safety evaluations will include a physical examination, vital signs, ECG, clinical laboratory tests (clinical chemistry, hematology, urinalysis, and serology), lung function, urine drug tests, urine cotinine tests, and alcohol breath tests, FSH tests (post-menopausal females) and serum and urine pregnancy tests (females only).

On-study safety evaluations will include a symptom-driven physical examinations, vital signs, ECG, clinical laboratory tests (clinical chemistry, hematology, and urinalysis), lung function, and urine pregnancy tests (females only).

AEs spontaneously reported by the subjects or observed by the Investigator or other study personnel will be documented and monitored from the time of first product use after successful completion of the check-in (Day -2) events for Test Visit 1 through the end of the Follow-up Period. Any prior and concomitant medications taken from 30 days prior to Screening through the Follow-up Period will also be recorded.

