# JUUL® Product Use

Subjects in the JUUL® arm will begin using the product following the demonstration and training on Day -2 and will continue to use the product through 23:00 on Day -1.

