#### 7.4 Adverse Events

All adverse events (AEs) occurring during this clinical trial will be coded using the Medical Dictionary for Regulatory Activities (MedDRA®), Version 21.0.

All AEs captured in the database will be listed in by-subject data listings including verbatim term, coded term, product, severity, relationship to study product, and action; however, only product use-emergent AEs (PUEAEs) will be summarized.

A PUEAE is defined as an AE that is starting or worsening at the time of or after the first randomized study product use. Each PUEAE will be attributed to a study product based on the onset date and time of the AE.

If the onset time of an AE is missing and the onset date is the same as the first study product use date, then the AE will be considered product use emergent in the study product. If onset time of an AE is missing and the onset date does not fall on a study product use date, then the AE will be considered product use emergent for the last study product administered. If the onset date of an AE is missing, then the AE will be considered product use emergent, unless the onset date is known to have occurred within or between specific product use days.

PUEAEs will be tabulated by System Organ Class (SOC) and Preferred Term. Summary tables will include number of subjects reporting the AE and as percent of number of subjects used study product by product. The number of AEs will be tabulated in a similar manner. Tables which tabulate the number of PUEAEs by severity and relationship to study product will also be included.

In addition, adverse events occurred during baseline period on Day -2 and day -1 will be summarized separately.

Serious adverse events (SAEs), if present, will also be listed. Applicable narratives will be included in the CSR.

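### The safety population opens on Day -1, one day after JUUL use and AE recording begin, so a subject who uses JUUL only on Day -2 falls outside it

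*SAP*

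**What the plan says.** SAP 4.1.1 reads "The safety population will include all subjects with at least one reported product use from Day -1", and protocol 7.2.1 has the same sentence.

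JUUL exposure starts a day earlier. SAP 6.1.1 says that JUUL subjects "will begin using the product following the demonstration and training on Day -2". Footnote 5 to protocol Table 3, the JUUL schedule, says: "All subjects will use the assigned study product from completion of check-in events through discharge from the study". Check-in is on Day -2.

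AE capture also starts on Day -2. Protocol 6.9.2 states: "All events occurring after use of study products on Day -2 must be recorded on the eCRF as AEs". SAP Section 3 has AEs "documented and monitored from the time of first product use after successful completion of the check-in (Day -2) events for Test Visit 1".

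The two documents word emergence differently. Protocol 7.6 counts an AE "starting or worsening at the time of or after the first study product use on Day -2"; SAP 7.4 counts one "starting or worsening at the time of or after the first randomized study product use". For the JUUL arm both dates are Day -2.

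SAP 7.4 also undertakes to list every AE in the database, to express AE counts "as percent of number of subjects used study product by product", and to summarize Day -2 and Day -1 AEs separately.

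**The concern.** A safety population should contain everyone exposed to a study product from the moment AEs are recorded. Here it opens one day late for the one arm that receives its assigned product on Day -2. Early withdrawal after first use is a setting in which an AE may be the reason for leaving. If it is, the event drops out of the numerator and the subject out of the denominator, and the AE rate of the comparator e-cigarette is understated. The two documents would also give the programmer conflicting instructions on whether to show that subject at all.

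**Working it through.** The plan gives no figure for this point, so the check is first a reading of the rules and then an illustration.

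**Rule check.** Inclusion requires the last product use to fall on or after Day -1.

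- JUUL use on Day -2 only: excluded now; included if the start is Day -2.
- JUUL use on Day -2 and Day -1: included either way.
- JUUL use through Day 1: included either way.

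Only the Day -2-only user is lost, and an AE after that use is emergent under both definitions.

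**Does another population catch this subject?** No. SAP 4.1.2 limits ITT to the main study, and JUUL subjects take part only in the PK sub-study (SAP Section 3). The PK population (SAP 4.1.4) needs an evaluable profile, and JUUL profiles are taken on Day 1.

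**Which outputs carry the label?** In the SAP Section 9 list, every numbered Section 14.3 table is titled Safety Population: AEs, SAEs, abnormal laboratory values, and the laboratory, vital sign, ECG and spirometry summaries. The discontinuation listing (16.2.1) and AE listings (16.2.7) are labelled the same way. The narratives heading (14.3.3) and the list of subjects excluded from analysis (16.2.3) carry no population label.

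**Size, by assumption.** The planned JUUL arm is 20 (SAP Section 3). Suppose one subject is lost, and x of the other 19 have the event.

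- The lost subject had the event. Understatement = (x + 1)/20 − x/19 = (19 − x)/380.
  - x = 0: 0/19 = 0% (exact 95% CI 0 to 17.6%) against 1/20 = 5.0% (0.1 to 24.9%); 5.0 points.
  - x = 5: 26.3% against 30.0%; 14/380 = 3.7 points.
  - x = 10: 52.6% against 55.0%; 9/380 = 2.4 points.
- The lost subject did not have the event. The current rule overstates the rate by x/19 − x/20 = x/380, which is 10/380 = 2.6 points at x = 10.
- Two subjects lost, both with the event and no others affected: 0/18 = 0% (0 to 18.5%) against 2/20 = 10.0% (1.2 to 31.7%).
- One lost with the event and replaced, as protocol 4.6 allows, with no others affected: 0/20 against 1/21 = 4.8%.

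**The case against.** The case on the other side is that this is a one-day wording mismatch affecting a hypothetical subject in a PK-only comparator arm. Most of that stands, and it rules out several stronger readings.

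- A reader might infer that the rule removes precisely those who leave because of a first-day reaction. It does not: it depends on product use, not on outcome. It also drops someone who withdraws consent on Day -2 without an AE, and it keeps someone who reacts on Day -2 but uses the product once on Day -1.
- A reader might infer that the event would vanish from all safety output. SAP 7.4 and protocol 7.6 both promise listings of all AEs in the database, and SAP 7.4 adds narratives and a Day -2/Day -1 summary. The labelled titles conflict with that text, so the subject's fate in the listings is unclear rather than settled. The exclusion from the labelled Section 14.3 tables is clear if the definition is applied as written.
- A reader might infer that each lost subject costs 5 points. That is the maximum for one lost subject in a planned arm of 20, as the working shows.
- A reader might infer that the myblu safety conclusion is at risk. The safety objective (number 10) concerns myblu, and myblu use starts on Day 1, so every myblu user qualifies already.

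It is also fair to say that the recording and emergence rules define events, whereas 4.1.1 defines subjects, so this is a misalignment rather than a direct contradiction between definitions. The conflict inside the SAP is firmer: 7.4 takes all users of a product as the denominator, while the AE tables apply a population that omits some of them.

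**Conclusion.** The point holds, at low severity. As written, the safety population starts one day after JUUL exposure and AE capture, and neither document repairs this elsewhere. A Day -2-only JUUL user is excluded from the tables labelled Safety Population whatever the reason for leaving.

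The number affected is probably very small and may be zero. All sizes above rest on assumed counts and the planned 20 subjects. With one lost subject who had an AE, the JUUL rate is understated by at most 5 percentage points, which is well within the exact interval for an arm of this size. Bias in one direction needs the further assumption that Day -2 departures are driven by AEs, for which the documents offer no data.

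**What to change.** In protocol 7.2.1 and SAP 4.1.1, replace Day -1 with Day -2 and specify first product use after check-in. That wording matches the start of AE monitoring in SAP Section 3 and avoids counting smoking at home before check-in. The titled tables and listings then agree with SAP 7.4.

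The edit is one day number and a short qualifier in each document, with one small cost. It also admits myblu and continue-smoking subjects who smoked their usual brand on Day -2 and left during baseline. Report their events in the Day -2/Day -1 summary already planned in SAP 7.4, and state that they do not enter the denominators for myblu Products A to D. The difference between the protocol 7.6 and SAP 7.4 emergence definitions for those two arms would remain after this edit and should be reconciled at the same time.

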# 4.1.2 Intent-to-Treat (ITT) Population

The ITT population will consist of randomized subjects in the main study with at least one documented product-use experience from Day 1, irrespective of their compliance of the product-use to which they were randomized.

### 4.1.3 Per-Protocol Population

The PP population (main study) is a subset of the ITT population who meet the requirements below. Separate populations for Product Use Period 1 (PP28/29) and Product Use Period 2 (PP56/57) will be established based on data collected during each of those periods.

The PP population will be used (in addition to the ITT population) only in the analysis of primary biomarkers of exposure (COHb in plasma and NNAL, 3-HPMA, and S-PMA in urine) and in the product use analysis.

#### mybluTM and continue-smoking arms

- Have no protocol deviations significantly impacting the integrity of the analysis or interpretation of the individual endpoint under consideration (e.g., compromised urine samples, use of prohibited medications impacting the endpoint)
- Have a daily product use response rate of at least 70% during the product use period
- Have a positive urine cotinine test at each scheduled assessment.

#### mybluTM arm

• Self-report reducing cigarette consumption by at least 90% of that reported at baseline

- Have exhaled CO values  $\leq 8$  ppm at each scheduled post-baseline assessment
- Have post-baseline urine NNAL values reduced by  $\geq 75\%$  from baseline.

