3. SUMMARY OF STUDY DESIGN

3.1 Design and Procedures

This will be an open-label, partially-randomized, parallel-arm, multi-site study in healthy adult smokers, consisting of the main study and a PK sub-study.

The main study will assess BoE, BoPH, physiologic effects, and subjective effects with use of *my*bluTM e-cigarettes relative to continuing to smoke combustible cigarettes. To account for potential attrition, up to 175 subjects are planned to be randomized into the *my*bluTM arm (with approximately 43 subjects intended to be assigned to each *my*bluTM e-liquid) and up to 40 subjects will be randomized into the continue-smoking arm. Baseline study assessments will be made during use of subjects' usual brand combustible cigarettes during the initial test visit through the morning of Day 1. All subjects in the *my*bluTM and continue-smoking arms will return to the clinic site for test visits scheduled to occur on Days 14, 28, 42, and 56 for post-baseline study assessments, compliance checks, and product dispensing and return. The subset of subjects participating in the PK sub-study (described below) will also complete selected biomarker assessments (NNAL, NNN, 3-HPMA, CEMA, HMPMA, S-PMA, nicotine equivalents) on Days 3 and 4.

Subjects randomized to the *my*bluTM arm will participate in an in-clinic product acclimation period from Days 1 to 3. The acclimation period will afford the subjects the opportunity to try each of the four *my*bluTM e-liquids in order to become accustomed to their use and to determine those that they would be willing to use during the study. Initial product assignment for each subject will be based on preference as a method to enhance compliance. To further improve compliance through Day 56, at the end of Test Visit 3, subjects using a *my*bluTM

product may be allowed to choose to switch to the alternate nicotine strength of their current flavor, to switch to the alternate flavor with the same nicotine strength as their initial choice, or to continue using the same e-liquid selected initially. This method for initial flavor assignment and the opportunity to re-select after 28 days of use is based on natural experimentation that consumers experience when choosing an e-cigarette flavor.

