7.5 Statistical Analysis

7.5.1 Primary Endpoints

Comparisons of the Day 28 visit primary BoE change-from-baseline values between the continue-smoking arm and each mybluTM e-liquid product selected at Day 1 will be made using a linear mixed model ANOVA. The ITT population will be used as the primary analysis population and an analysis using the PP population will be used as a supportive analysis.

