#### **Product Use Compliance**

Subject self-reported product use will be used as a measure of compliance. The clinic staff will monitor the frequency with which subjects complete the daily product use entries leading up to each Test Visits 2 through 5.

Biochemical verification of compliance will also be performed. Exhaled CO and urine cotinine will be used as methods of verifying compliance in real-time.

NNAL is a tobacco-specific nitrosamine with a longer half-life than CO, thus may provide an estimate of compliance over a long period of time by comparison of the post-baseline values to the baseline values. As this will be measured in a bioanalytical assay, real-time monitoring will not be possible and the verification will be completed at the end of the study.

NNAL will be considered as an additional exploratory variable for compliance.

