Table 14.2.2.2.1.4	Summary of Urine NNAL Adjusted for Urine Creatinine by Study Product and Study Day (ITT Population)	
Table 14.2.2.2.1.5	Summary of Urine NNAL Adjusted for Urine Creatinine Change From Baseline by Study Product and Study Day (ITT Population)	
Table 14.2.2.2.1.6	Summary of Urine NNAL Adjusted for Urine Creatinine Percent Change From Baseline by Study Product and Study Day (ITT Population)	
Table 14.2.2.2.1.7	Summary of Urine NNAL Amount Excreted by Study Product and Study Day (PP Population)	
Table 14.2.2.2.1.8	Summary of Urine NNAL Amount Excreted Change From Baseline by Study Product and Study Day (PP Population)	
Table 14.2.2.2.1.9	Summary of Urine NNAL Amount Excreted Percent Change From Baseline by Study Product and Study Day (PP Population)	

J -1	
Table 14.2.2.2.1.10	Summary of Urine NNAL Adjusted for Urine Creatinine by Study Product and Study Day (PP Population)
Table 14.2.2.2.1.11	Summary of Urine NNAL Adjusted for Urine Creatinine Change From Baseline by Study Product and Study Day (PP Population)
Table 14.2.2.2.1.12	Summary of Urine NNAL Adjusted for Urine Creatinine Percent Change From Baseline by Study Product and Study Day (PP Population)
Table 14.2.2.2.2.1	Statistical Comparison of Urine NNAL 24-hour Amount Excreted Change From Baseline Between my blu TM and Continuous Smoking by Study Day (ITT Population)
Table 14.2.2.2.2.2.2	Statistical Comparison of Urine NNAL 24-hour Amount Excreted Change From Baseline Between my blu TM and Continuous Smoking by Study Day (PP Day28/29 Population)
Table 14.2.2.2.2.3	Statistical Comparison of Urine NNAL 24-hour Amount Excreted Change From Baseline Between my blu TM and Continuous Smoking by Study Day (PP Day56/57 Population)
Table 14.2.2.2.2.4	Statistical Comparison of Urine NNAL 24-hour Amount Excreted Change From Baseline Between my blu TM and Continuous Smoking by Study Day (PP Day56/57 Population – Sensitivity Analysis)

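### The per-protocol set admits myblu subjects only if NNAL fell by at least 75%, then tests NNAL against controls who face no such limit, so for NNAL it cannot independently support the ITT result

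*SAP*

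**What the plan says.** SAP 4.1.3 and Protocol 7.2.3 give the same entry rules. Both main-study arms need no deviation that compromises the endpoint, a diary response rate of at least 70%, and a cotinine condition: "Have a positive urine cotinine test at each scheduled assessment". Three further conditions apply to the myblu arm alone: a self-reported cut in cigarettes of at least 90%, exhaled CO of at most 8 "ppm at each scheduled post-baseline assessment", and the NNAL condition, "Have post-baseline urine NNAL values reduced by" at least 75% from baseline.

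On use, SAP 4.1.3 says "The PP population will be used (in addition to the ITT population) only in the analysis of primary biomarkers of exposure" (COHb, NNAL, 3-HPMA and S-PMA) and in the product use analysis. Protocol 7.5.1 and SAP 6.7.1 make ITT primary and say "the PP population will be used as a supportive analysis". The NNAL table list in SAP Section 14.2.2.2 includes a myblu comparison with "Continuous Smoking by Study Day (PP Day28/29 Population"), and two more for the Day 56/57 PP set. SAP 6.7.1 and the comparison-table shells in SAP 10.2 call for a difference in least-squares means, a 95% confidence interval and a p-value.

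On the status of NNAL, SAP 6.1.1 says "NNAL will be considered as an additional exploratory variable for compliance". SAP 6.1.2 lists the same 75% threshold among the compliance variables. Protocol 3.1 adds that PK sub-study subjects "will also complete selected biomarker assessments (NNAL, NNN, 3-HPMA, CEMA, HMPMA, S-PMA, nicotine equivalents) on Days 3 and 4".

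**The concern.** The marker that decides who enters one arm of the PP set is also an endpoint tested between arms in that set. A myblu subject whose NNAL fell by 40% is removed; a control with any NNAL change stays. The set therefore shows a large NNAL fall in the myblu arm whether most subjects switched or only a few did.

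At stake is the supportive role. A reader who sees ITT and PP agree on NNAL will take the second result as corroboration, although the entry rule has supplied most of it. Protocol 1.3 says the data may go into premarket submissions, where supportive results are read alongside the primary ones.

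**Working it through.** **Inputs.** Protocol 7.1 gives NNAL baseline 340 ng, change-from-baseline SDs of 178 (test) and 133 (control), 29 per group, one-sided alpha 0.0125, a planned effect of 50%, and stated power 0.9623. It also cites a 5-day in-clinic study in which exclusive use lowered the primary biomarkers by about 60% to 95%, and cutting cigarettes by about 30% lowered them by about 13% to 27%. The 75% threshold is from SAP 4.1.3.

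**The plan's own figure.** Planned effect = 0.50 × 340 = 170 ng. Standard error = √[(178² + 133²)/29] = √1702.5 = 41.3 ng. A two-sample t-test with unequal variances (noncentral t, Satterthwaite df about 51.8) gives power 0.9623, as stated. The normal approximation gives 0.9699.

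**The floor.** Suppose the rule applies to 24-hour mass at the tested visit. Each admitted subject i has fall_i ≥ 0.75 × baseline_i. Averaging, mean fall ≥ 0.75 × mean baseline. At 340 ng this is 255 ng, or 255/170 = 1.5 times the planned effect. It needs only the entry rule and a baseline.

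**How PP and ITT relate.** Let a share s switch with proportional fall f, and let the others fall by g, all from 340 ng. Then:

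- ITT mean fall = 340 × [s·f + (1 − s)·g]
- PP mean fall = 340 × f
- PP/ITT = f / [s·f + (1 − s)·g]

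I take f from 0.75 (the threshold) to 0.95, and g from 0 (no change) to 0.27 (the top of the cited range for partial reduction). Both ranges, and s, are assumptions.

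| Share switching | ITT mean fall (ng) | PP mean fall (ng) | PP/ITT |
|---|---|---|---|
| 20% | 51–138 | 255–323 | 2.0–5.0 |
| 40% | 102–184 | 255–323 | 1.6–2.5 |
| 60% | 153–231 | 255–323 | 1.3–1.7 |

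The largest ratios have g = 0, where PP/ITT = 1/s. The smallest have f = 0.75 and g = 0.27; at s = 0.2 that is 0.75/(0.15 + 0.216) = 2.05. The PP column does not move with s.

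**When ITT reaches the planned effect.** Set s·f + (1 − s)·g = 0.5, so s = (0.5 − g)/(f − g). With f = 0.95, g = 0.27: 0.23/0.68 = 34%. With f = 0.75, g = 0: 0.5/0.75 = 67%. Below that share the ITT fall is under 170 ng while PP still shows at least 255 ng.

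**How few subjects suffice.** Take a 255 ng difference, the protocol SDs, 29 controls and no control change. The normal approximation gives power 0.79 with 5 admitted myblu subjects (standard error √(178²/5 + 133²/29) = 83.3 ng) and 0.97 with 10. Keeping SD 178 in a selected set is an assumption.

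**What is left undefined.** SAP 6.2.3 derives percent change for 24-hour mass and for creatinine-adjusted values, and names mass for the statistical analysis; SAP 4.1.3 does not say which of the two the 75% uses. SAP 4.1.3 ties each PP set to data from its own period, and outside the PK sub-study the only post-baseline NNAL collections are at Days 28/29 and 56/57. The open visit is the Day 3–4 collection in PK sub-study subjects (up to 20 per e-liquid), which falls inside Period 1 as Protocol's Definition of Terms sets it out.

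**The case against.** The strongest defence is that the asymmetry is deliberate and reasoned. Controls are assigned to keep smoking, so an NNAL-fall rule for them would select non-adherers. Protocol 6.3.3 explains that self-report alone may overstate compliance, and the criteria are pre-specified and identical in both documents. A 75% fall also lies within the 60% to 95% cited for exclusive use, and the tables show n per comparison. All of this stands, and it justifies describing verified switchers. It does not turn a between-arm test of the verifying marker into separate evidence, and n shows how many were excluded, not what the difference would be without the rule.

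Several stronger readings are tempting but unsupported:

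- *The rule fixes the PP result.* It sets a minimum. The fall above 75% and the control-arm change are free, so the between-arm difference is not predetermined.
- *The PP fall will be five times the ITT fall.* That needs 20% switching and no change at all in everyone else. Protocol 7.1 cites falls of 13% to 27% with partial reduction, hence the ranges above.
- *The PP test of COHb is equally void.* The CO rule acts on exhaled CO at check-in, a related but separate measurement from the afternoon blood sample. Selection through a related marker also touches 3-HPMA and S-PMA, so there is no consistent ground for dropping the COHb p-value alone.
- *A specific false-positive rate follows.* A simulation can give 69% to 85% rejection, but only by assuming that the same 10% to 50% of both arms, controls included, cut NNAL by about 90%. The documents give no basis for that.
- *The rule names no visit and leaves three variables open.* SAP 4.1.3 and 6.2.3 narrow this to two variables and the Day 3–4 value.

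**Conclusion.** The point holds for NNAL. The PP myblu mean fall is at least 75% of the PP baseline mean by construction (255 ng at the planning baseline, 1.5 times the 170 ng used for power), provided the rule is applied to 24-hour mass at the tested visit. PP agreement with ITT on NNAL is therefore not independent support. The PP/ITT ratios and the 34% to 67% switching range are illustrations that rest on assumed falls; the floor is not. For COHb, 3-HPMA and S-PMA the selection is indirect and the documents support no size.

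A reader might infer that the primary conclusion is compromised. It is not: ITT is primary, does not use these rules, and no success criterion depends on PP. The harm is confined to supportive evidence, but it is built in and cheap to remove. The mismatch between SAP 6.1.1 and 4.1.3 is one of wording; nothing in 6.1.1 removes the entry rule.

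**What to change.** In SAP 4.1.3 and 6.7.1 and Protocol 7.2.3 and 7.5.1:

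1. Label the set 'biochemically verified switchers'.
2. Report NNAL in it descriptively, without a between-arm p-value, and do not cite it as support for the ITT NNAL result.
3. Keep the PP comparisons of COHb, 3-HPMA and S-PMA, with a note that the set is selected after randomisation, in one arm, on correlated markers.
4. State that the 75% rule uses 24-hour mass (the analysed variable) at Day 28/29 for the first PP set and Day 56/57 for the second, and whether the Day 3–4 PK sub-study value counts.
5. Align the wording on NNAL in SAP 6.1.1 with its role as an entry condition in 4.1.3.

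No new data are needed, and the ITT analysis does not change. The cost is some relabelling, a few clarifying sentences, and the loss of an inferential PP result for NNAL, one of the four primary biomarkers.
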